## **Summary of Changes**

New protocol version and date: version 5.0, see date of last approval on cover page Previous protocol version and date: version 4.0 dated 22-Jan-2020

Substantial protocol changes	changes	
Description of the substantial modification	Protocol sections concerned	Rationale for the substantial modification
Additional criterion for patient withdrawal has been added: a patient must be withdrawn from the study if he / she is unable to attend two or more protocol-specified study visits due to COVID-19	9.10 Patient withdrawal	COVID-19 situation. In line with FDA guidelines, the sponsor has assessed study protocol version 4.0 focusing on patient safety and data integrity in the context of the COVID-19. Specifically, for each visit described in the schedule of assessments (ToA – Table 2), the sponsor assessed if visits could be performed virtually (via either phone or videoconference) to reduce patients travelling to the study site. After thorough evaluation of assessments performed during scheduled visits and potential alternatives (such as use of a local laboratory), the sponsor concludes that physical patient visits to the site remain essential to adequately provide for patient safety and to appropriately evaluate tumor growth. While blood chemistry and hematology assessments of ECOG, patient-reported questionnaires and vital signs cannot be assessed remotely. The sponsor acknowledges that patients who participate in this study do not have any standard curative or life prolonging therapy available (eligibility criterion #2). Weighing the COVID-19 risk against potential benefit for patients without life prolonging therapeutic options, the sponsor has decided to keep the study open with the visit schedule unchanged. However, a patient must be discontinued from the study if two (2) visits have been missed as essential safety assessments could be ediscontinued from the study if two (2) visits have been missed as essential safety assessments.

	
 
SAEs resulting in death
 

	
 
SAEs resulting in discontinuation
 

	• SAEs resulting in dose reduction or dose interruption
	• Frequency, time to onset and severity of AEs
	• Changes from baseline in safety parameters
	
 
Additional Efficacy: TTR, DOR, TTF and PFS, evaluated according to the response evaluation criteria in solid tumors (RECIST), version 1.1 [2, 3]
 
Pharmacokinetics: Bimiralisib plasma concentrations. To be reported separately.
 

F _1_4	
Exploratory	• ctDNA:
endpoints	
 
ctDNA sequences and levels in patient plasma
 

	Pre-cancerous keratinocytic skin lesions:
	• Number and size of index lesions
	NOTCH protein levels
	
 
Protein levels
 
Protein levels of cleaved NOTCH1 (NICD) as determined by immunohistochemistry (IHC)
 

Version 5.0

Study design	This is an open-label, single arm, two-stage study to evaluate the efficacy and safety of bimiralisib in patients with r/m HNSCC containing NOTCH1 LOF mutations. The study will be conducted in $1 - 4$ centers. Patients will be treated with 140 mg bimiralisib p.o. once daily on two consecutive days followed by five days without treatment in consecutive 7-day treatment blocks. Patients will follow this iterative "2d on / 5d off" treatment scheme until unacceptable toxicity, tumor progression, patient's request for withdrawal, investigator judgment or death, whichever comes first.
	Stage 1 of the study will enroll 10 patients. Response evaluation of Stage 1 patients will be performed in an ongoing manner (ongoing analysis, OA). If two or more patients in stage 1 show a confirmed partial or confirmed complete response, stage 2 may enroll 19 patients. If less than two patients in stage 1 show a confirmed partial or confirmed complete response during the OA, a formal futility analysis will be performed once all 10 patients in Stage 1 have been assessed for their response to bimiralisib. If futility is confirmed as per defined criteria, the study will be stopped.
	The study will end when all patients have been treated for 6 months or have discontinued study participation for any reason, whichever comes first.
Patient population	Adult patients with recurrent or metastatic HNSCC with NOTCH1 LOF mutations

Inclusion criteria	Patients may be included in the study if they meet all the below inclusion criteria:
	
 
≥ 18 years of age.
 
Histologically or cytological confirmed diagnosis of HNSCC, for which no standard curative or life prolonging therapy is available.
 
Available CLIA-certified sequencing results of the NOTCH1 gene in HNSCC tumor material. The tumor must harbor a NOTCH1 LOF mutation as confirmed by central review (MD Anderson Cancer Center, MDACC).
 
ECOG performance status of ≤ 2
 
Adequate bone marrow, liver, and renal functions, defined as:
 

	• Platelet count $\ge 100 \ge 10^{9/1}$ , absolute neutrophil count (ANC) $\ge 1.5 \ge 10^{9/1}$ , hemoglobin $\ge 9 \ g/dL$ .
	
 
ALT and AST ≤ 2.5 upper limit normal (ULN), or < 5 x ULN if liver metastases are present; serum total bilirubin ≤ ULN or 1.5 x ULN if liver metastases are present or total 3 x ULN with direct bilirubin ≤ ULN in patients with well-documented Gilbert syndrome.
 

	• Glomerular filtration rate (GFR) ≥ 30 ml/min (Cockcroft-Gault)
	
 
6. Fasting plasma glucose (FPG) ≤ 150 mg/dL.
 
7. Patient must understand the investigational nature of this study and sign an independent ethics committee/institutional review board approved written informed consent form prior to any study related procedure.
 

	
 
Measurable disease according to RECIST version 1.1 [2, 3]
 
The patient has already received standard platinum chemotherapy and immunotherapy. Patients who cannot tolerate platinum or immunotherapy or are ineligible for them, based on the judgement of the treating oncologist, will be eligible to enroll on this trial.
 

	10. Patients of reproductive potential must agree to use effective contraception from screening until 90 days after discontinuing study treatment.

Exclusion criteria	Patients will be excluded from the study if they meet any of the below exclusion criteria:
	
 
Has an oncogenic KRAS mutation.
 
Has received any anti-cancer treatment including hormonal and investigational agents within 21 days prior to first dose of bimiralisib.
 

	3. Patients who receive gamma knife radiosurgery for brain metastases or whole brain radiation are eligible if gamma knife radiosurgery was completed > 2 weeks before treatment is started or whole brain radiation was performed > 4 weeks before treatment is started, and are clinically stable.
	4. Known hypersensitivity to any of the excipients of bimiralisib
	
 
capsules.
 
5. Major surgery within 28 days prior to first dose of bimiralisib or persisting side effects that have not improved to NCI-CTCAE grade 1 or better.
 

	6. Poorly controlled diabetes mellitus, steroid-induced diabetes mellitus, FPG > 150 mg/dL.
	7. Concomitant treatment with medicinal products that increase the pH (i.e. reduce acidity) of the upper gastrointestinal tract, including, but not limited to, proton-pump inhibitors (e.g. Omeprazole), H2-antagonists (e.g. Ranitidine) and antacids is restricted. Patients may be enrolled in the study after a washout period sufficient to terminate their effect.
	8. Active tobacco or e-cigarette smoking habit. Non-smoker status will be confirmed by cotinine test at screening in all patients with a history of smoking. Additional cotinine tests may be administered at the discretion of the treating investigator if current smoking is suspected.
	

9. Patients who are on (or will require) prolonged systemic corticosteroid treatment during the study (see section 8.2.3.2).

	
 
10. Use of oral herbal preparations or herbal medications during the study period. Patient should stop using oral herbal medications 7 days prior to the first dose of bimiralisib
 

	11. Concurrent severe and/or uncontrolled medical conditions that would, in the investigator's judgment, contraindicate patient participation in the clinical study or require concomitant anti- cancer drugs (e.g., active or uncontrolled severe infection, chronic active hepatitis, immuno-compromised, acute or chronic pancreatitis, uncontrolled high blood pressure, interstitial lung
	disease, etc.). 12. Has other active malignancies that require systemic treatment.

	
 
13. Has a known history of HIV infection (testing not mandatory).
 
14. Any of the following cardiac abnormalities: 
 
History of, or current, documented congestive heart failure (New York heart association functional classification iii - iv), documented cardiomyopathy
 
Symptomatic (NYHA class II or higher) left ventricular ejection fraction (LVEF) < 40% as determined by multiple gated acquisition (MUGA) scan or echocardiogram (echo)
 
Myocardial infarction ≤ 6 months prior to enrolment
 
Unstable angina pectoris
 
Serious uncontrolled cardiac arrhythmia
 
Symptomatic pericarditis
 
 
 
15. Impaired gastrointestinal (GI) function or GI disease that may significantly alter the absorption of study drug.
 
16. Patient has a history of non-compliance to medical regimen or inability to grant consent.
 
17. Pregnant or nursing (lactating) women.
 
18. Medically documented history of an active major depressive episode, bipolar disorder (I or II), obsessive-compulsive disorder, schizophrenia, a history of suicidal attempt or ideation, or homicidal ideation (immediate risk of doing harm to others) or ≥ CTCAE grade 3 anxiety
 
19. History of interstitial pneumonitis or patients who require chronic oxygen supplementation.
 

Investigational therapy	140mg bimiralisib (capsules of 20mg and 80mg, supplier PIQUR Therapeutics AG, Basel, Switzerland) p.o. once daily on two consecutive days followed by five days without treatment in consecutive 7-day treatment blocks. Patients will follow this iterative "2d on / 5d off" treatment scheme until unacceptable toxicity, disease progression, patient's request for withdrawal, investigator judgment or death, whichever comes first.
Efficacy assessments	Radiological tumor assessments will be performed by CT or MRI according to a standard protocol at baseline (BL), every 6 weeks, and at the end of treatment (EOT). PET scans are not permitted for efficacy assessment. All reasonable effort should be made for radiological tumor assessments at a study site to be performed by the same person. ORR, TTR, DOR, TTF and PFS will be determined according to RECIST version 1.1 [2, 3].

Version 5.0

Safety assessmentsContinuous serious adverse event (SAE) monitoring from date of consent until 30 days after the last dose of bimiralisib. Continuous adverse event (AE) monitoring (as per NCI-CTCAE leasification, version 5.0) from first dose of bimiralisib until 30 days after the last dose of bimiralisib. Blood chemistry, hematology, vital signs, physical examination, ECG and HDALe, Patient Health Questionnaire (PHQ)-9 and General Anxiety Disorder (GAD)-7 questionnaire. Pregnancy test as appropriate.Other assessments• ECOG • PK blood samples • Dermatological evaluation • ctDNA blood samplesOngoing analysis (OA)Stage 1 of the study will enroll 10 patients. Response evaluation as per RECIST 1.1 of Stage 1 patients will be performed in an ongoing manner (ongoing analysis, OA). If the OA reveals that two or more Stage 1 patients show a confirmed partial or confirmed complete response as per RECIST 1.1, Stage 2 may be opened for enrollment without a formal futility analysis.Interim Analysis for futilityIf less than two patients in stage 1 show a confirmed partial or confirmed complete response during the OA, a formal futility analysis will be performed once all 10 patients in Stage 1 have been assessed for their response to bimiralisib. If futility is confirmed as per defined criteria, the study will be stopped.Analysis populationsPer protocol set: all patients treated per protocolData analysisSafety set: all patients who have received at least one dose of bimiralisib frequency and percentage of the ORR with a two- sided 95%-confidence interval Secondary endpoints (except pharmacokinetics): Safety : all safety data will be summarized in a descriptive manner Additional efficacy parameters: time to event data will be summarized using the Kaplan-Me	Safaty	Continuous serious adverse event (SAE) monitoring from data of consent	
Disorder (GAD)-7 questionnaire. Pregnancy test as appropriate.Other assessments• ECOG • PK blood samples • Dermatological evaluation • ctDNA blood samplesOngoing analysis (OA)Stage 1 of the study will enroll 10 patients. Response evaluation as per RECIST 1.1 of Stage 1 patients will be performed in an ongoing manner (ongoing analysis, OA). If the OA reveals that two or more Stage 1 patients show a confirmed partial or confirmed complete response as per RECIST 1.1, Stage 2 may be opened for enrollment without a formal futility analysis.Interim Analysis for futilityIf less than two patients in stage 1 show a confirmed partial or confirmed complete response during the OA, a formal futility analysis will be performed once all 10 patients in Stage 1 have been assessed for their response to bimiralisib. If futility is confirmed as per defined criteria, the study will be stopped.Analysis populationsSafety set: all patients who have received at least one dose of bimiralisib Per protocol set: all patients treated per protocolData analysisPrimary endpoint: Frequency and percentage of the ORR with a two- sided 95%-confidence interval Secondary endpoints (except pharmacokinetics): Safety: all safety data will be summarized in a descriptive manner Additional efficacy parameters: time to event data will be summarized using the Kaplan-Meier methodology. Other efficacy endpoints will be summarized descriptivelyPharmacokinetics (to be reported separately): descriptive statistics for PK parameters (e.g., AUC, Cmax, t  / 2 , etc)Exploratory endpoints (to be reported separately): descriptive statistics		until 30 days after the last dose of bimiralisib. Continuous adverse event (AE) monitoring (as per NCI-CTCAE classification, version 5.0) from first dose of bimiralisib until 30 days after the last dose of bimiralisib.	
assessments• PK blood samples • Dermatological evaluation • ctDNA blood samplesOngoing analysis (OA)Stage 1 of the study will enroll 10 patients. Response evaluation as per RECIST 1.1 of Stage 1 patients will be performed in an ongoing manner (ongoing analysis, OA). If the OA reveals that two or more Stage 1 patients show a confirmed partial or confirmed complete response as per RECIST 1.1, Stage 2 may be opened for enrollment without a formal futility analysis.Interim Analysis for futilityIf less than two patients in stage 1 show a confirmed partial or confirmed complete response during the OA, a formal futility analysis will be performed once all 10 patients in Stage 1 have been assessed for their response to bimiralisib. If futility is confirmed as per defined criteria, the study will be stopped.Analysis populationsSafety set: all patients who have received at least one dose of bimiralisib Per protocol set: all patients treated per protocolData analysisPrimary endpoint: Frequency and percentage of the ORR with a two- sided 95%-confidence intervalSecondary endpoints (except pharmacokinetics): Safety: all safety data will be summarized in a descriptive manner Additional efficacy parameters: time to event data will be summarized using the Kaplan-Meier methodology. Other efficacy endpoints will be summarized descriptivelyPharmacokinetics (to be reported separately): descriptive statistics for PK parameters (e.g., AUC, Cmax, t  / 2 , etc)Exploratory endpoints (to be reported separately): descriptive statistics			
Ongoing analysis (OA)Stage 1 of the study will enroll 10 patients. Response evaluation as per RECIST 1.1 of Stage 1 patients will be performed in an ongoing manner (ongoing analysis, OA). If the OA reveals that two or more Stage 1 patients show a confirmed partial or confirmed complete response as per RECIST 1.1, Stage 2 may be opened for enrollment without a formal futility analysis.Interim Analysis for futilityIf less than two patients in stage 1 show a confirmed partial or confirmed complete response during the OA, a formal futility analysis will be performed once all 10 patients in Stage 1 have been assessed for their response to bimiralisib. If futility is confirmed as per defined criteria, the study will be stopped.Analysis populationsSafety set: all patients who have received at least one dose of bimiralisib Per protocol set: all patients treated per protocolData analysisPrimary endpoint: Frequency and percentage of the ORR with a two- sided 95%-confidence interval Secondary endpoints (except pharmacokinetics): Safety: all safety data will be summarized in a descriptive manner Additional efficacy parameters: time to event data will be summarized using the Kaplan-Meier methodology. Other efficacy endpoints will be summarized descriptivelyPharmacokinetics (to be reported separately): descriptive statistics for PK parameters (e.g., AUC, Cmax, t  / 2 , etc)Exploratory endpoints (to be reported separately): descriptive statistics		• ECOG	
• ctDNA blood samplesOngoing analysis (OA)Stage 1 of the study will enroll 10 patients. Response evaluation as per RECIST 1.1 of Stage 1 patients will be performed in an ongoing manner (ongoing analysis, OA). If the OA reveals that two or more Stage 1 patients show a confirmed partial or confirmed complete response as per RECIST 1.1, Stage 2 may be opened for enrollment without a formal futility analysis.Interim Analysis for futilityIf less than two patients in stage 1 show a confirmed partial or confirmed complete response during the OA, a formal futility analysis will be performed once all 10 patients in Stage 1 have been assessed for their response to bimiralisib. If futility is confirmed as per defined criteria, the study will be stopped.Analysis populationsSafety set: all patients who have received at least one dose of bimiralisib Per protocol set: all patients treated per protocolData analysisPrimary endpoint: Frequency and percentage of the ORR with a two- sided 95%-confidence interval Secondary endpoints (except pharmacokinetics): Safety: all safety data will be summarized in a descriptive manner Additional efficacy parameters: time to event data will be summarized using the Kaplan-Meier methodology. Other efficacy endpoints will be summarized descriptivelyPharmacokinetics (to be reported separately): descriptive statistics for PK parameters (e.g., AUC, Cmax, t1/2, etc)Exploratory endpoints (to be reported separately): descriptive statistics	assessments	• PK blood samples	
analysis (OA)Energy of the one of a particular of a particular of a performed in an ongoing manner (ongoing analysis, OA). If the OA reveals that two or more Stage 1 patients show a confirmed partial or confirmed complete response as per RECIST 1.1, Stage 2 may be opened for enrollment without a formal futility analysis.Interim Analysis for futilityIf less than two patients in stage 1 show a confirmed partial or confirmed complete response during the OA, a formal futility analysis will be performed once all 10 patients in Stage 1 have been assessed for their response to bimiralisib. If futility is confirmed as per defined criteria, the study will be stopped.Analysis populationsSafety set: all patients who have received at least one dose of bimiralisib Per protocol set: all patients treated per protocolData analysisPrimary endpoint: Frequency and percentage of the ORR with a two- sided 95%-confidence interval Secondary endpoints (except pharmacokinetics): Safety: all safety data will be summarized in a descriptive manner Additional efficacy parameters: time to event data will be summarized using the Kaplan-Meier methodology. Other efficacy endpoints will be summarized descriptivelyPharmacokinetics (to be reported separately): descriptive statistics for PK parameters (e.g., AUC, Cmax, t½, etc)Exploratory endpoints (to be reported separately): descriptive statistics			
for futilityIn loss many two patients in stage 1 show a commuted patient of committee complete response during the OA, a formal futility analysis will be performed once all 10 patients in Stage 1 have been assessed for their response to bimiralisib. If futility is confirmed as per defined criteria, the study will be stopped.Analysis populationsSafety set: all patients who have received at least one dose of bimiralisib Per protocol set: all patients treated per protocolData analysisPrimary endpoint: Frequency and percentage of the ORR with a two- sided 95%-confidence interval Secondary endpoints (except pharmacokinetics): Safety: all safety data will be summarized in a descriptive manner Additional efficacy parameters: time to event data will be summarized using the Kaplan-Meier methodology. Other efficacy endpoints will be summarized descriptively Pharmacokinetics (to be reported separately): descriptive statistics for PK parameters (e.g., AUC, Cmax, t½, etc)Exploratory endpoints (to be reported separately): descriptive statistics		RECIST 1.1 of Stage 1 patients will be performed in an ongoing manner (ongoing analysis, OA). If the OA reveals that two or more Stage 1 patients show a confirmed partial or confirmed complete response as per RECIST 1.1, Stage 2 may be opened for enrollment without a formal	
populationsDate of per protocol set: all patients who have received at reast one dose of onlinearistData analysisPrimary endpoint: Frequency and percentage of the ORR with a two- sided 95%-confidence intervalSecondary endpoints (except pharmacokinetics): Safety: all safety data will be summarized in a descriptive manner Additional efficacy parameters: time to event data will be summarized using the Kaplan-Meier methodology. Other efficacy endpoints will be summarized descriptivelyPharmacokinetics (to be reported separately): descriptive statistics for PK parameters (e.g., AUC, Cmax, t 1/2 , etc)Exploratory endpoints (to be reported separately): descriptive statistics	-	complete response during the OA, a formal futility analysis will be performed once all 10 patients in Stage 1 have been assessed for their response to bimiralisib. If futility is confirmed as per defined criteria, the	
Data analysisPrimary endpoint: Frequency and percentage of the ORR with a two- sided 95%-confidence intervalSecondary endpoints (except pharmacokinetics): Safety: all safety data will be summarized in a descriptive manner Additional efficacy parameters: time to event data will be summarized using the Kaplan-Meier methodology. Other efficacy endpoints will be summarized descriptivelyPharmacokinetics (to be reported separately): descriptive statistics for PK parameters (e.g., AUC, Cmax, t 1/2 , etc)Exploratory endpoints (to be reported separately): descriptive 	· · · ·		

 
Safety: all safety data will be summarized in a descriptive manner
 
Additional efficacy parameters: time to event data will be summarized using the Kaplan-Meier methodology. Other efficacy endpoints will be summarized descriptively
 
Pharmacokinetics (to be reported separately): descriptive statistics for PK parameters (e.g., AUC, Cmax, t/2, etc)
 
Exploratory endpoints (to be reported separately): descriptive statistics for ptatistics
 
	Data analysis	Primary endpoint: Frequency and percentage of the ORR with a two-	

 
Additional efficacy parameters: time to event data will be summarized using the Kaplan-Meier methodology. Other efficacy endpoints will be summarized descriptively
 
Pharmacokinetics (to be reported separately): descriptive statistics for PK parameters (e.g., AUC, Cmax, t/2, etc)
 
Exploratory endpoints (to be reported separately): descriptive statistics
 
		Secondary endpoints (except pharmacokinetics):	

 
using the Kaplan-Meier methodology. Other efficacy endpoints will be summarized descriptively
 
Pharmacokinetics (to be reported separately): descriptive statistics for PK parameters (e.g., AUC, Cmax, t/2, etc)
 
Exploratory endpoints (to be reported separately): descriptive statistics
 
		Safety: all safety data will be summarized in a descriptive manner	
PK parameters (e.g., AUC, Cmax, t  / 2 , etc)         Exploratory endpoints (to be reported separately): descriptive statistics		using the Kaplan-Meier methodology. Other efficacy endpoints will be	
statistics			
Keywords HNSCC, NOTCH1 LOF, bimiralisib			
	Keywords	HNSCC, NOTCH1 LOF, bimiralisib	

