### **3** Study purpose, objectives and endpoints

The main purpose of this study is to determine the objective response rate (ORR) of patients with r/m HNSCC harboring *NOTCH1* LOF mutations to oral bimiralisib. The ORR comprises patients with confirmed partial response (PR) or confirmed complete response (CR) as per RECIST version 1.1 [2, 3].

The study objectives and related endpoints are summarized in Table 3.

Protocol PQR309-009

PIQUR Therapeutics AG - Confidential

Version 5.0

Amendment date: see date of last approval

Table 3:Objectives and related endpoints

I able 3: Objectives and related enapoints		
Objective(s)	Endpoint(s)	Assessment Description
Primary		
To determine the objective response rate (ORR) of patients with r/m HNSCC harboring NOTCH1 LOF mutations to oral bimiralisib	ORR: comprised of all patients who achieved a confirmed partial or a confirmed complete response	Section 9.3
Secondary		
To evaluate the safety of bimiralisib in patients with r/m HNSCC harboring NOTCH1 LOF mutations	
 
Overall SAEs
 
Overall SAEs
 
SAEs resulting in death
 
SAEs resulting in discontinuation
 
SAEs resulting in dose reduction or dose interruption
 
SAEs resulting in dose reduction or dose interruption
 
Changes from baseline in:
 
body weight,
 
vital signs,
 
ECOG performance status,
 
ECO,
 
hematology,
 
hematology,
 
biochemistry and
 
Patient Health Questionmaire (PHQ)-9 and General Anxiety Disorder (GAD)-7 mood scale score
 
	Section 9.4

Page 23 of 81

Protocol PQR309-009 PI	PIQUR Therapeutics AG - Confidential	Version 5.0
	Amendm	Amendment date: see date of last approval
Objective(s)	Endpoint(s)	Assessment Description
To evaluate additional clinical efficacy parameters of bimiralisib in patients with r/m HNSCC harboring NOTCH1 LOF mutations	TTR, DOR, TTF and PFS, evaluated according to RECIST version 1.1 [2, 3].	Section 9.3
To evaluate the pharmacokinetics of bimiralisib in patients with r/m HNSCC harboring NOTCH1 LOF mutations	Bimiralisib plasma concentrations. To be reported separately.	Section 9.6
Exploratory		
To determine if bimiralisib affects the size and number of pre-cancerous keratinocytic lesions (actinic keratosis)	Number and size of index lesions	Section 9.7.1

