### 7.2 Treatment interruptions and bimiralisib dose reductions

For patients who do not tolerate the protocol-specified dose, dose adjustments are permitted in order to allow the patient to continue bimiralisib treatment. Changes in dosing schedule are not allowed. Any changes in bimiralisib administration must be recorded on the CRF. Whenever possible, any dose adjustment of bimiralisib should be discussed between the investigator and the study sponsor prior to implementation.

As a first step to manage bimiralisib-related toxicities, bimiralisib treatment should be temporarily interrupted.

All treatment interruptions, discontinuations and dose reductions must be based on the worst preceding AE as graded by the NCI common terminology criteria for AE (NCI-CTCAE version 5.0). Once the bimiralisib dose has been reduced, re-escalation is not permitted.

Guidelines for treatment interruptions and bimiralisib dose reductions are described in Table 4.

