## Table 4: Treatment interruptions and dose reductions for adverse events (except hyperglycaemia) considered related to bimiralisib by the treating physician

Reason	Treatment change
Non-haematological AE Grade 4	Stop bimiralisib treatment permanently.
Haematological AE Grade 4	Interrupt bimiralisib treatment. If AE resolves to baseline or CTCAE grade 1 within 7 days, patients may resume treatment at the reduced dose of 100mg. If AE resolves within 8 to 14 days, patient may resume treatment at the reduced dose of 100mg if agreed between investigator and sponsor. If AE does not resolve to baseline or CTCAE grade 1 within 14 days, bimiralisib treatment must be discontinued permanently.
Grade 3 AE	Interrupt bimiralisib treatment. If AE resolves to baseline or CTCAE grade 1 within 7 days, patient may resume treatment at 140mg. If AE resolves to CTCAE grade 1 within 8 to 14 days, patient may resume treatment at the reduced dose of 100mg. If AE does not resolve to baseline or CTCAE grade 1 within 14 days, bimiralisib treatment must be discontinued permanently.
Any non-haematological AE grade 2	Continue bimiralisib treatment. Dose reduction at the discretion of the treating physician

Patients who after dose interruption do not tolerate bimiralisib treatment at 100 mg must be permanently discontinued. If during the first three months on study, a patient cannot restart at the 100 mg dose level within 14 days, this patient is not evaluable for the primary endpoint, and the investigator must discuss the individual benefit-risk evaluation of this patient with the sponsor before restarting dosing. These patients may be replaced.

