# 10.4.2.5 Tolerability

Tolerability will be studied in terms of dose reductions and drug interruptions due to AE. Reasons for dose reductions and interruptions will be listed and summarized by treatment.

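### The safety endpoint for stopping treatment counts serious events only, and no named safety summary covers permanent discontinuation due to non-serious adverse events

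*Protocol*

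**What the plan says.** Protocol section 1.1 (Synopsis, secondary endpoints) lists "SAEs resulting in discontinuation" among the safety endpoints. The companion endpoint, also in Table 3 of section 3, is "SAEs resulting in dose reduction or dose interruption". The synopsis list also has an endpoint on all AEs, "Frequency, time to onset and severity of AEs", which does not mention the action taken with study drug.

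The rules that lead to treatment changes use a different criterion. Section 7.2 states: "All treatment interruptions, discontinuations and dose reductions must be based on the worst preceding AE as graded by the NCI common terminology criteria". Table 4 in that section has the scope "Treatment interruptions and dose reductions for adverse events (except hyperglycaemia) considered related to bimiralisib by the treating physician" and works by grade. Hyperglycaemia is handled in sections 12.6.1 and 12.6.1.1, by glucose level and grade, and those rules include discontinuation. Section 12.2.3.1 warns that severity and seriousness are separate properties.

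On analysis, section 10.4.2.5 says: "Tolerability will be studied in terms of dose reductions and drug interruptions due to AE". It adds that the reasons for reductions and interruptions are listed and summarised. Permanent discontinuation is not named there.

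**The concern.** Safety is the first secondary objective of a single-arm trial, and how often patients stop for toxicity is one of the main tolerability figures a reader will look for. Under the protocol's rules a patient can stop permanently for an AE that never meets a seriousness criterion. Examples are a related grade 3 event that has not resolved within the period allowed in Table 4, or high-grade hyperglycaemia that does not improve in time under section 12.6.1.1. Such a patient is outside the discontinuation endpoint as worded.

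The protocol itself uses discontinuation as evidence. Section 4.5.2.5 does not class gastrointestinal toxicity as an important risk, partly because those events very rarely end treatment. A serious-only count would not let this trial update that statement for non-serious events.

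**Working it through.** The plan states no figure on this point, so there is none to reproduce. The check sets the endpoint list against the treatment-change rules and the planned analyses.

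**Step 1: which events lead to treatment changes?**
- Related AEs other than hyperglycaemia: CTCAE grade decides (section 7.2, Table 4). Permanent stopping is tied to grade 4 non-haematological events and to grade 3, or haematological grade 4, events that do not resolve in time. Seriousness is not a condition.
- The row "Any non-haematological AE grade 2" says to continue treatment, with "Dose reduction at the discretion of the treating physician". It can lead to a reduction but does not require a change.
- Hyperglycaemia: glucose level and grade decide (sections 12.6.1 and 12.6.1.1). Section 4.5.2.8 reports it in almost 50% of exposed patients.
- Unacceptable AE is also a general ground for withdrawal from treatment (section 9.10), again without a seriousness condition.

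**Step 2: which planned outputs capture each change when the AE is non-serious?**

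| Planned output | Reduction or interruption | Permanent discontinuation |
|---|---|---|
| Serious-only endpoints (synopsis, Table 3) | No | No |
| Tolerability analysis (10.4.2.5) | Yes, any AE | Not named |
| AE tables (10.4.2.2) | By class or term, grade, type and relation; action taken not named | Same |
| Time to treatment failure (10.4.1) | Not applicable | Counted, but not separated by reason, and on the per-protocol set |
| Listings (10.4.2.1, 10.4.2.2) | Recoverable by hand | Recoverable by hand |

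The one change without a named summary on the safety set is permanent discontinuation due to a non-serious AE.

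**Step 3: does time to treatment failure fill the gap?** No. It pools progression, AE, withdrawal of consent, new treatment and death. Section 10.4.1 also places all efficacy analyses on the per-protocol set. Under section 7.2, a patient who cannot restart at the lower dose level within 14 days in the first three months is not evaluable for the primary endpoint and may be replaced. Some toxicity stops could therefore be absent from that set. How many cannot be said, because section 10.3.2 leaves the exclusions to the data handling plan and SAP.

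**Step 4: how large could the gap be?** The documents give neither the rate of stopping for an AE nor the serious share, so this is an illustration on assumed values. Let N be the number of patients, d the proportion who stop for an AE, and s the share of those stops caused by serious AEs.

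Stops = N × d; captured = N × d × s; missed = N × d × (1 − s); share missed = 1 − s.

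N runs from 29 (planned) to 35 (maximum enrolment, section 10.2). Assume d = 15% to 25%.
- Stops: 29 × 0.15 = 4.35 to 35 × 0.25 = 8.75, or about 4 to 9 patients.
- With s assumed at 20% to 50%: captured 4.35 × 0.20 = 0.9 to 8.75 × 0.50 = 4.4; missed 4.35 × 0.50 = 2.2 to 8.75 × 0.80 = 7.0.
- With s assumed at 10% to 70%: captured 4.35 × 0.10 = 0.4 to 8.75 × 0.70 = 6.1; missed 4.35 × 0.30 = 1.3 to 8.75 × 0.90 = 7.9; share missed 30% to 90%.

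The count is small in every case. The share depends wholly on s.

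**The case against.** The best defence is that little is lost. Section 10.4.2.5 covers reductions and interruptions for any AE, so two of the three kinds of treatment change are already summarised without a seriousness limit. All treatment-emergent AEs are tabulated, all safety data are listed, changes in administration go on the CRF (section 7.2), and the sponsor is told of each treatment discontinuation (section 9.10). A row for serious events that led to stopping is accurate for what it claims to count, and a narrow endpoint can stand beside a wider tolerability analysis. Section 10.4 leaves detailed data handling to the SAP, and the SAP text available covers only hypotheses and sample size, so a further table may be planned elsewhere.

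Most of this stands, and it limits the point to permanent discontinuation. A listing is not a summary, though, and nothing in the available text commits the sponsor to one for non-serious stops.

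A reader might infer that most treatment changes escape reporting. The documents do not support that. They give no serious share, grade 4 events may often also be serious, the grade 2 row of Table 4 says to continue treatment, and section 10.4.2.5 covers reductions and interruptions. Sections 4.5.2.1 and 4.5.2.4 report no serious anaemia and mostly non-serious fatigue. That makes a substantial non-serious share plausible but does not measure it, and it concerns events rather than treatment stops.

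**Conclusion.** The point holds in a limited form. The discontinuation endpoint is defined on serious events, the rules for stopping do not depend on seriousness, and no named safety-set summary in the available text counts permanent stops due to non-serious AEs. The endpoint list and section 10.4.2.5 also use different event definitions for reductions and interruptions, which is worth aligning although the data will be reported.

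The size is unknown: the share missed is one minus the serious share, which the documents do not give. It would not be right to conclude that the planned row misstates toxicity. It is narrow rather than false, and would mislead only if read as the overall rate of stopping for AEs. Nor does the point reach the primary endpoint, the sample size or the two-stage decision rule.

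The conclusion assumes that no fuller SAP or table shell already contains a summary of discontinuations due to any AE. If one does, only the endpoint wording needs aligning.

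**What to change.** In the synopsis and Table 3, define the two endpoints as AEs, serious and non-serious, resulting in discontinuation, and AEs, serious and non-serious, resulting in dose reduction or interruption. Show the serious subset of each as a sub-row, so that the present endpoints remain visible. In section 10.4.2.5, add the number and percentage of patients on the safety set with permanent discontinuation due to an AE, with the reasons, and carry the same definition into the SAP.

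The cost is a wording change and one extra table row. AEs and changes in drug administration are already recorded on the CRF and discontinuations are already notified to the sponsor, so no new data collection should be needed. The reported discontinuation rate may look less favourable. No dosing, interruption or stopping rule changes.
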